## 8.4 HANDLING OF MISSING DATA

In general, observed data will be used in statistical analysis without imputation, unless missing data will jeopardize the integrity of the study or pose a problem in the validity of the analysis. A data-as-observed (DAO) approach will be used to evaluate the primary endpoint. Uncertain viral load measurements that are below the lower limit of quantification (LLOQ) will be set to  $0.5 \times \text{LLOQ}$  in the viral load summaries and indicated as BLQ in the listings. Impact of missing data will be assessed, and sensitivity analysis will be performed when deemed appropriate. Details will be described in the SAP.

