#### **4.1. Sample Size**

The sample size for this study is up to 60 subjects and each cohort will include 20 subjects, allocated 3:1 (AT-752:placebo). In Low et al (Low 2014), the observed standard deviations (SD) for VLR, defined as mean change from baseline viral load on days 2,3, and 4, ranged from 0.75 (N=26) to 1.07 (N=24). Taking into account that the VLR endpoint in the study was based on an average of 3 measurements and assuming that there is some correlation between measurements on days 2 through

4, we consider power to detect a true effect at a single time point using a one-sided 0.10 level test (unadjusted for multiple comparisons) with N=15 per arm for SD in a range from 1 to 1.75:

True standard deviation	Effect (log 10 copies/ml) with 80% power (N=15 vs. 15)	Effect (log 10 copies/ml) with 80% power (N=15 vs. 5)
1	0.8	1.1
1.25	1	1.4
1.5	1.2	1.7
1.75	1.4	2.0

Based on the above table, there is 80% power to detect a true treatment effect (versus placebo) on change-from-baseline viral load of 1 log10 at a time point if the true SD is 1.25 for comparison of groups with N=15 each. The analogous power to detect a 1 log10 effect for a within cohort comparison is 59%. Furthermore, if true SD is in the range from 1 to 1.75, the probability that the observed effect would be 0.5 log10 or larger is low (in range from 0.09 to 0.22) if there is no treatment effect, i.e., an observed effect of 0.5 or larger might be considered suggestive of a signal. Interpretation of results will consider the totality of the data.

In the event there is at least one subject who withdraws without post-baseline virology data, with the exception of those who withdraw for safety or tolerability, enrollment may remain open or extended at each dose level/cohort to enroll additional randomization block(s) of 4 patients (3:1) to increase the likelihood that at least 15 active and 5 placebo subjects with evaluable virology data are included in each cohort. Any additional patients will be randomized through the same centralized randomization process. All statistical analysis will be based on actual enrolled subjects.

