### **8.1 Primary Efficacy**

#### **8.1.1 Primary Endpoint**

The primary objective of this study is to evaluate the antiviral activity of AT-752 compared with placebo on change from baseline in DENV viral load (DENV RNA as measured by RT-qPCR) based on the log-10 scale at specified time points:

$$y_i = v_i - v_0$$

where  $v_i$  is the log10 DENV viral load measured at timepoint  $t_i$  and  $v_0$  is the log10 DENV viral load measured at baseline. Viral load measurements that are below the lower limit of quantification (LLOQ) will be set to  $0.5 \times \text{LLOQ}$  in the analysis.

Change from baseline in DENV viral load ( $y_i$ ) will be analyzed with repeated measures mixed model using the method of restricted maximum likelihood (REML). The model will include baseline viral load, treatment, time, and treatment-by-time interaction as fixed factors. An unstructured covariance matrix will be specified for the repeated statement. In case a mixed model with unstructured (UN) covariance matrix fails to converge, a compound symmetry (CS) structure will be used as an alternative. If neither of these converges, independent (ID) structure will be used. If none of these converges, the change from baseline by scheduled time point (ANOVA, Kruskal-Wallis) analysis will be presented as the primary analysis. The treatment group least squares mean (LSM) estimates for mean change from baseline and treatment group differences at each time point, with 80% CI, 95% CI and p-value will be presented.

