### 8.1.2 Primary Endpoint Supportive Analyses

The primary endpoint will also be analyzed using the same method in the as-treated population.

The following viremia descriptively summarized by treatment arm, with comparison method indicated in parentheses:

- Change from baseline in log10 viral load by scheduled time point (Kruskal-Wallis). Along with the Kruskal-Wallis test, a one-way ANOVA will be used to compare treatment effect separately at each time point.
- Proportion of measurements above the lower limit of quantification (Fisher exact)

All viremia data will be listed and individual profiles of viremia over time will be presented for each subject. Viremia levels below the lower limit of quantification will be considered as 0 in the log10 viral load summaries and indicated as BLQ in the listings.

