### 10. Missing data handling

In general, observed data will be used in statistical analysis without imputation, unless missing data will jeopardize the integrity of the study or pose a problem in the validity of the analysis. A data-as-observed (DAO) approach will be used to evaluate the primary endpoint. Uncertain viral load measurements that are below the lower limit of quantification (LLOQ) will be set to  $0.5 \times \text{LLOQ}$  in the viral load summaries and indicated as BLQ in the listings. If subjects withdraw early, the outcome measure up to point of study withdrawal will be used.

Impact of missing data will be assessed, and ad-hoc sensitivity analysis will be performed when deemed appropriate. No imputation is planned for the primary efficacy analysis, as the study allows replacement when a subject withdraws without any post-baseline virology data and a mixed model will be used. If at a particular time point, the amount of missing data in the AT-752 arm is greater than 10% due to dropout, the impact will be assessed. In this case, an ad-hoc sensitivity analysis using multiple imputations will be performed using the Markov chain Monte Carlo (MCMC) method to impute non-monotone missing data, and a copy reference (i.e. placebo) approach to impute monotonic missing data in the AT-752 arm.

For safety data, missing and partial dates will be programmatically handled according to the following standards: if the day of the month is missing for any date used in a calculation, the 1st of

the month will be used to replace the missing date unless the calculation results in a negative time duration (e.g., date of resolution cannot be prior to date of onset; if replacing resolution date with the 1st of the month results in a negative duration, the resolution date will be set to the onset date). In this case, the date resulting in 0 time duration will be used. These standards are also used if both month and day are missing (Jan 1 unless negative time duration, durations will be reset to 1 day).

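### Setting on-treatment values below LLOQ to half the LLOQ in the primary mixed model pulls the estimated log10 effect toward zero, proportionally more for stronger doses, and no censored-data analysis is planned beside it

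*SAP*

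**What the plan says.** SAP 8.1.1 defines the primary outcome as change from baseline in log10 DENV RNA. It fits a REML repeated-measures model with unstructured covariance: "The model will include baseline viral load, treatment, time, and treatment-by-time interaction as fixed factors". For that analysis, "Viral load measurements that are below the lower limit of quantification (LLOQ) will be set to" 0.5 x LLOQ. Protocol 8.4 and SAP 10 use the same constant for viral load summaries ("Uncertain viral load measurements that are below the lower limit of quantification (LLOQ) will be set to" 0.5 x LLOQ).

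SAP 8.1.2 gives a different rule: "Viremia levels below the lower limit of quantification will be considered as 0 in the log10 viral load summaries". If no covariance structure converges, SAP 8.1.1 makes the by-time-point ANOVA/Kruskal-Wallis analysis primary. That analysis is described in SAP 8.1.2, the section with the zero rule.

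For interpretation, SAP 4.1 says that "there is 80% power to detect a true treatment effect (versus placebo) on change-from-baseline viral load of 1 log10 at a time point" if the SD is 1.25, and that "an observed effect of 0.5 or larger might be considered suggestive of a signal".

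Three planned analyses bear on values below LLOQ: a Fisher exact comparison of the share of quantifiable measurements, a Kruskal-Wallis test at each time point (both SAP 8.1.2), and Kaplan-Meier time to clearance (SAP 12). The sensitivity analyses in SAP 10 address missing data and dropout. None treats a value below LLOQ as censored.

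**The concern.** A value below LLOQ says only that the true load is somewhere under the limit. Replacing it with one fixed number just under the limit and analysing it as measured puts a floor under the outcome. A drug that works drives more patients to that floor, so its arm loses more of its true decline than placebo does, and the least squares mean difference is too small.

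This matters because the study is meant to inform dose selection, and SAP 4 calls its confidence intervals and p-values descriptive. The size of the estimate therefore carries most of the interpretation, and it is read against a planning effect of 1 log10 and a signal mark of 0.5 log10. If stronger doses lose proportionally more, doses will also look more alike than they are.

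**Working it through.** **Inputs from the documents.** One-sided 0.10 test, SD 1 to 1.75, planning effect 1 log10 at SD 1.25, 15 vs 15 for pooled placebo and 15 vs 5 within a cohort (SAP 4.1); substitution of 0.5 x LLOQ (SAP 8.1.1).

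**Assumptions.** The LLOQ, the baseline load and the share below LLOQ are not given. The placebo share is therefore varied, and the active share follows from the effect and SD. Log10 viral load is taken as normal with equal SD in both arms, and the plan's SD for the change is used for the load itself.

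**Step 1: the plan's own figures.** Two-sample t-test power for 1 log10 at SD 1.25 is 81.0% (15 vs 15) and 59.2% (15 vs 5), against the stated 80% and 59%. The tabulated effects come out as 0.787, 0.984, 1.180 and 1.377, and as 1.123, 1.403, 1.684 and 1.964, all matching after rounding. The chance of an observed 0.5 or more with no effect is 0.086 to 0.217 at 15 vs 15, against the stated 0.09 to 0.22. The planning figures are sound; they make no allowance for values below LLOQ.

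**Step 2: mean under the half-LLOQ rule.** Put log10(LLOQ) at 0, so the substituted value is log10(0.5) = -0.301. For an arm with mean mu and share below LLOQ P = Phi(-mu/SD), the expected analysed mean is

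E = P x (-0.301) + mu x (1 - P) + SD x phi(mu/SD).

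Example with 20% of placebo below LLOQ, SD 1.25, true effect 1.0:

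- Placebo: mu = 1.25 x 0.8416 = 1.052, P = 0.20, phi = 0.280. E = -0.060 + 0.842 + 0.350 = 1.131.
- Active: mu = 0.052, P = 0.483, phi = 0.399. E = -0.146 + 0.027 + 0.498 = 0.380.
- Difference: 1.131 - 0.380 = 0.75, a loss of 25%. The average share is (20 + 48)/2 = 34%.

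| Below LLOQ, placebo / active | Average share | Estimate of a true 1.0 | Loss |
|---|---|---|---|
| 1% / 6% | 4% | 0.99 | 1% |
| 5% / 20% | 12% | 0.93 | 7% |
| 10% / 32% | 21% | 0.87 | 13% |
| 20% / 48% | 34% | 0.75 | 25% |
| 30% / 61% | 45% | 0.64 | 36% |
| 40% / 71% | 55% | 0.54 | 46% |
| 50% / 79% | 64% | 0.44 | 56% |

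At a 30% placebo share the estimate is 0.62 to 0.66 for SD 1 to 1.75. Over 560 combinations of effect, SD and share, the loss was always positive. It averaged 7 percentage points below the mean share of the two arms (range 14 below to 1 above).

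**Step 3: by strength of effect.** With 20% of placebo below LLOQ and SD 1.25, true effects of 0.5, 1, 1.5 and 2 are estimated as 0.41, 0.75, 1.02 and 1.20 (losses 18, 25, 32 and 40%). A true gap of 1.0 between a 1-log and a 2-log dose appears as 1.20 - 0.75 = 0.45.

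**Step 4: simulation at 15 vs 15.** A baseline-adjusted analysis at one visit (assumed baseline SD 1, slope 0.3) stands in for the mixed model with complete data. It gave 0.93, 0.86, 0.74, 0.65 and 0.45 at placebo shares of 5, 10, 20, 30 and 50%, close to the formula. Variance shrinks too, so power fell only from 81% to 77% at a 20% share and from 82% to 68% at 50%. A left-censored normal (Tobit) likelihood gave median estimates of 0.92 to 1.03 across the simulations run.

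**Step 5: the zero rule.** With the SAP 8.1.2 value of 0 on the log10 scale, an assumed LLOQ of 2 to 3.5 log10 and a 20% placebo share, a true 1.0 becomes 1.23 to 1.66. At a 50% share and an LLOQ of 2 log10 it becomes 0.92. In most settings tried, this rule inflates the effect.

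**The case against.** **The size is unknown and may be small.** Patients enter within 60 hours of fever onset, and the first fixed post-dose samples are at 24 and 48 hours (Protocol 3.1.4, 4.1). If only 1 to 5% of placebo values are below LLOQ then, the loss is 1 to 7%. The 0.44 figure needs half of placebo below LLOQ, and nothing in the documents establishes that share. This stands.

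**Other planned analyses would reveal the effect.** A drug that pushes more patients below LLOQ would show in the Fisher, Kruskal-Wallis and clearance analyses. SAP 4.1 also calls 0.5 only suggestive and asks for the totality of the data. This stands as mitigation, but shares, ranks and times do not repair the log10 difference, which is the reported primary estimate.

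**The censored fit is not more accurate overall.** In simulations at 15 vs 15, root mean squared error for substitution against the censored fit was 0.43 to 0.44 against 0.48 to 0.49 at a 20% placebo share. At 50% it was 0.62 to 0.63 against 0.78 to 1.07, and in one simulation 37% of trials had two or fewer quantified active values. This stands too. It argues for a supportive analysis with a limit on its use, not for replacing the primary model.

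**Stronger readings that a reader might infer.** One is that the effect shrinks by the full share of patients below LLOQ; the table shows it does not (20%/48% gives 25%). Another is that any fixed constant shrinks the effect; the zero rule usually does the opposite. A third is that the trial would lose most of its power; the simulated fall is modest.

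**Conclusion.** The concern holds in a bounded form. Half-LLOQ substitution in the primary model biases the log10 difference toward zero. The relative loss is usually somewhat less than the average share below LLOQ in the two arms, and it is greater in arms with larger effects. The estimate of a true 1.0 log10 ranges from 0.99 when 1% of placebo values are below LLOQ to 0.44 when 50% are. At 50% the expected estimate lies under the plan's own 0.5 mark.

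These figures rest on normality, equal SDs and assumed shares. The documents do not support naming one of them as the bias in this trial, nor treating 0.5 as a go/no-go rule that the bias would trip. No dose-against-dose test is planned, so the flattening between doses affects how the estimates are read side by side, not a formal comparison.

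The direction is certain only for the half-LLOQ rule. Because SAP 8.1.2 uses 0, and its by-time-point analysis can become primary, even the direction is open in the fallback case. Adding a supportive analysis and settling on one rule is worth doing before unblinding; the primary model need not change.

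**What to change.** 1. Keep the SAP 8.1.1 mixed model as primary.
2. Prespecify in SAP 8.1.1, and in SAP 12 for viral titre, a supportive left-censored normal regression on treatment and baseline, fitted separately at each on-treatment visit. Values below LLOQ contribute the probability of lying below LLOQ. Name the visits, and state whether the sample taken 8 to 24 hours after the last dose counts as on-treatment.
3. Fit it only where each arm has a minimum number of quantified values, set before unblinding.
4. Report it beside the least squares mean difference, with the percentage below LLOQ by arm on the same line. The Fisher analysis already needs those percentages.
5. Reconcile the 0.5 x LLOQ rule (Protocol 8.4, SAP 8.1.1, SAP 10) with the zero rule in SAP 8.1.2. State which applies to the descriptive summaries, and which applies if the by-time-point ANOVA/Kruskal-Wallis becomes primary.

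The cost is extra programming and a few table columns. The added analysis relies on normality and is more variable when most values are censored, which is why it is supportive and limited by item 3. No change to sampling or sample size is needed.

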### **8.1 SAMPLE SIZE CALCULATIONS**

The sample size for this study is approximately 60 subjects. Each of the 3 cohorts will include 20 subjects (15 subjects receive AT-752 and 5 subjects receive placebo).

In Low et al ([Low 2014](#)), the observed standard deviations for VLR, defined as mean change from baseline viral load on days 2, 3, and 4, ranged from 0.75 (N=26) to 1.07 (N=24). Taking into account that the VLR endpoint in that study was based on an average of 3 measurements and assuming that there is some correlation between measurements on days 2 through 4, we consider power to detect a true effect at a single time point using a one-sided 0.10 level test (unadjusted for multiple comparisons) with N=15 per arm for standard deviations in a range from 1 to 1.75:

True standard deviation	Effect (log 10 copies/ml) with 80% power (N=15 vs. 15)  Comparison versus placebo pooled across 3 planned cohorts	Effect (log 10 copies/ml) with 80% power (N=15 vs. 5)  Comparison versus placebo within a cohort
1	0.8	1.1
1.25	1	1.4
1.5	1.2	1.7
1.75	1.4	2.0

Based on the above table, there is 80% power to detect a true treatment effect (versus placebo) on change-from-baseline viral load of 1 log10 at a time point if the true SD is 1.25 for comparison of groups with N=15 each. The analogous power to detect a 1 log10 effect for a within cohort comparison is 59%. Furthermore, if true SD is in the range from 1 to 1.75, the probability that the observed effect would be 0.5 log10 or larger is low (in range from 0.09 to 0.22) if there is no treatment effect, i.e., an observed effect of 0.5 or larger might be considered suggestive of a signal. Interpretation of results will consider the totality of the data.

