## **1. Introduction**

This Statistical Analysis Plan (SAP) provides details of the planned analyses and statistical methods used to evaluate antiviral activity, safety, pharmacokinetics (PK), and pharmacodynamics (PD) data for Study AT-02A-002. This SAP is written based on AT-02A-002 protocol Amendment 1, dated on 29 July 2022.

Dengue fever is a mosquito-borne illness that is caused by 4 distinct serotypes of ribonucleic acid (RNA) viruses (DENV-1, DENV-2, DENV-3, and DENV-4) belonging to the flavivirus genus.

Atea Pharmaceuticals is developing a novel purine nucleotide prodrug, AT-752, which is designed to treat patients that have been infected with the dengue virus (DENV). When dissolved, AT-752 releases the freebase **CCI** [REDACTED], which in a series of steps is converted to the intracellular active triphosphate metabolite, AT-9010 (triphosphate of AT-273, and therefore plasma AT-273 is considered a surrogate of intracellular AT-9010). A first-in-human study (Protocol AT-02A-001) was completed in 65 healthy adults in Australia to investigate the safety and pharmacokinetics (PK) (with embedded food effect and PK ethnic sensitivity evaluation) of AT-752. 41 subjects received single ascending doses (SAD), and 24 subjects participated in the multiple ascending dose (MAD) portion of the study. The first-in-human study supported dose selection for the current study.

The Phase 2 study AT-02A-002 will be conducted in adult patients with confirmed DENV infection and will investigate antiviral activity, safety, PK, and PD in this population. This study will be conducted in several dosing cohorts to enable dose selection for subsequent trials.

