#### 4. General Statistical Considerations

All statistical analyses will be conducted using statistical analysis system SAS® Version 9.4 or higher (SAS Institute, Cary, NC).

Analysis of the data from this study will be descriptive in nature. Confidence intervals and p-values will be descriptive due to small sample size in this study. N, mean, standard deviation, median, minimum and maximum, and 95% CI will be used for continuous data and number and percentage

will be used for categorical/count data, unless specified otherwise. No analysis will be performed until the data are unblinded.

All tables, listings, and figures will be presented by assigned treatment. The treatments below will be used for presentations:

- AT-752 750 mg TID
- AT-752 up to 1000 mg BID or TID
- AT-752 up to 1500 mg BID
- Placebo (pooled Cohort 1 through Cohort 3)

All data listings will be sorted by treatment and subject number. If a regimen is repeated in more than one cohort, the matching cohorts will be pooled as one treatment.

Unless otherwise specified, no algorithm for imputation of missing data will be employed.

Study days are calculated with respect to the first date of study drug exposure (First Dose Date) as below:

- If the assessment/observation date is on or after the first dose date, then  
Study Day = Assessment/Observation Date – First Dose Date + 1;
- Otherwise, Study Day = Assessment/Observation Date – First Dose Date

Baseline will be defined as the last non-missing assessment (including repeated and unscheduled assessments) before administration of the first dose of study drug, unless otherwise specified.

For summary of safety assessments, if there are repeated measurements at a time point, the first non-missing assessment at that time point will be used in the summary tables.

Unscheduled results will not be included in the summary tables, except for determining baseline, but will be presented in data listings.

The methodology and data handling specifications for PK data are detailed in Section 11.

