#### 4.2. Randomization, Stratification, and Blinding

The randomization schedule will be generated prior to the initiation of the study. Subjects who meet all inclusion and none of the exclusion criteria will be randomly assigned in a 3:1 ratio to either experimental drug or placebo. Randomization will be stratified by geographic region. Randomization numbers (in sequential order) will be assigned before the first dose of study drug is administered on Day 1. This is a double-blind study: the investigator and the subject will be kept blinded to the treatment allocation.

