#### **4.3. Analysis Population**

Primary endpoint analyses will be applied to the modified intent-to-treat population (mITT), which is defined as all randomized subjects who received at least 1 dose (full dose, unless assigned to placebo) of study drug (AT-752 or matching placebo) and have baseline and at least one post-baseline virology measurement. Change from baseline viral load (DENV RNA) will be compared between each AT-752 arm and a combined placebo group.

As-treated population is defined as all subjects who received at least 1 dose (full dose, unless assigned to placebo) of study drug (AT-752 or matching placebo) based on the actual treatment the patients received and had baseline and at least one post-baseline virology measurement.

The safety population will include all subjects who receive at least 1 dose of study drug.

The PK population will include all subjects who receive at least 1 dose of AT-752 and have sufficient concentration data to support accurate estimation of at least 1 PK parameter. PK parameter summaries will include only subjects in the PK population who have sufficient concentration measurement data to support estimation of the parameter. All subjects excluded from the PK population will be documented in the data listings.

The PD population will be the mITT population, which includes subjects who received at least 1 dose (full dose, unless assigned to placebo) of study drug and have baseline and at least 1 post-baseline viral load measurement.

The Per Protocol (PP) population will include the subset of the modified intent-to-treat population who completed study drug treatment without a major protocol violation that impact patient safety or data quality.

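### The primary model omits the stratification factor (region), and no virology summary shows placebo by cohort although every dose is compared with placebo pooled over sequential cohorts

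*SAP*

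**What the plan says.** - **Design.** SAP 4.2: "Randomization will be stratified by geographic region". Protocol section 3 describes three sequential cohorts. Each has 15 subjects on AT-752 and 5 on placebo, and the next one opens only after the Safety Review Committee has reviewed the last.
- **Primary model.** SAP 8.1.1: "The model will include baseline viral load, treatment, time, and treatment-by-time interaction as fixed factors". There is no region or cohort term. Protocol 8.3.1 has neither as well, and leaves the details to the SAP.
- **Comparator.** SAP 4.3: "Change from baseline viral load (DENV RNA) will be compared between each AT-752 arm and a combined placebo group". The treatment groups for all output in SAP 4 include a single placebo group, "Placebo (pooled Cohort 1 through Cohort 3".
- **Power.** The sample-size table in protocol 8.1 has a second column headed "Comparison versus placebo within a cohort". SAP 4.1 says of it: "The analogous power to detect a 1 log10 effect for a within cohort comparison is 59" percent. No analysis section carries that comparison out.
- **Use of the results.** SAP 1: "This study will be conducted in several dosing cohorts to enable dose selection for subsequent trials". SAP 4.1 adds that "an observed effect of 0.5 or larger might be considered suggestive of a signal". SAP 4 calls the confidence intervals and p-values descriptive.

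The supportive virology summaries (SAP 8.1.2) and the AUC, clearance and serotype summaries (SAP 12) are by treatment. The demographic summaries (SAP 6.1) list neither region nor cohort.

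**The concern.** Two gaps are linked. First, the plan randomises within region but does not analyse by region.

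Second, randomisation protects only the comparison inside a cohort, because a subject can be assigned only to the dose then open or to placebo. Pooling placebo brings in 10 comparators per dose who were enrolled at other times. If the course of viral load differs between cohorts after baseline adjustment, for instance because the regional mix changes, that difference enters the dose estimates. No planned summary would show it.

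The quantity most exposed is the difference between doses, which matters in a study meant to support dose selection.

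**Working it through.** **Inputs.** From the documents: 15 active and 5 placebo per cohort, three cohorts, one-sided 0.10, SD 1.25 (from the range 1 to 1.75), and the 0.5 log10 signal level. Assumed: a shift d of 0.25 or 0.5 log10 in one cohort, equal for active and placebo and left over after baseline adjustment; all cohorts full, no regimen repeated, no replacement block. Calculations are for a difference in means at one visit.

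**1. The plan's own figures.**
- SE against pooled placebo: 1.25 × √(1/15 + 1/15) = 0.456. SE against own-cohort placebo: 1.25 × √(1/15 + 1/5) = 0.645.
- Power for 1 log10 (noncentral t, one-sided 0.10): 0.810 for 15 vs 15 and 0.592 for 15 vs 5. The plan states 80% and 59%.
- Chance of an observed effect of 0.5 or more with no drug effect, 1 − Φ(0.5/SE): 0.086 at SD 1 and 0.217 at SD 1.75. The plan states 0.09 to 0.22. At SD 1.25 it is 0.137.

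**2. Effect of a shift d in one cohort.** The pooled placebo mean moves by (5/15)d = d/3.
- Shifted cohort's dose: d − d/3 = 2d/3.
- Each other dose: 0 − d/3 = −d/3.
- Shifted dose minus another dose: 2d/3 + d/3 = d.
- Average over the three doses: (2d/3 − d/3 − d/3)/3 = 0.

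| SD 1.25 | d = 0 | d = 0.25 | d = 0.5 |
|---|---|---|---|
| Bias, shifted dose | 0 | 0.17 | 0.33 |
| Bias, each other dose | 0 | −0.08 | −0.17 |
| Chance of ≥ 0.5 with no drug effect, shifted dose | 0.137 | 0.233 | 0.358 |
| Same, each other dose | 0.137 | 0.101 | 0.072 |
| Same, average of three | 0.137 | 0.145 | 0.167 |
| Shifted dose has the largest estimate, all doses equal | 0.33 | 0.57 | 0.78 |

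The chance entries are 1 − Φ((0.5 − bias)/0.456). The last row is from simulation.

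**3. Region.** With a stable regional mix, omission causes no bias. If two equal regions differ by g at every visit, the residual SD without the regional part is √(1.25² − g²/4): 1.225 for g = 0.5 and 1.146 for g = 1.0. Adding region would then cut the SE from 0.456 to 0.447 and 0.418. If the mix in one cohort moves by an assumed 40 points, d = 0.4g = 0.2 to 0.4, and the bias for that cohort's dose is 2d/3 = 0.13 to 0.27.

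**4. What an own-cohort comparison can do.** An additive shift cancels within a cohort, but the noise is larger.

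| SD 1.25 | Pooled placebo, d = 0 / 0.25 / 0.5 | Own-cohort placebo, any d |
|---|---|---|
| SE, dose vs placebo | 0.456 | 0.645 |
| At least one of three doses ≥ 0.5, no drug effect | 0.28 / 0.31 / 0.39 | 0.52 |
| A dose 0.5 log10 better (not the shifted one) ranks first | 0.778 / 0.655 / 0.475 | 0.567 |
| A dose 1.0 log10 better (not the shifted one) ranks first | 0.974 / 0.941 / 0.857 | 0.777 |

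The own-cohort 0.52 is 1 − (1 − 0.219)³; the other ranking and any-dose figures are simulated. Pooled placebo has the smaller mean squared error for the shifted dose until d = 1.5 × √(0.645² − 0.456²) = 0.68. Placebo in one cohort against the other two (5 vs 10, SE 1.25 × √0.3 = 0.685) flags d = 0.5 at a two-sided 20% level 31% of the time, against 20% by chance.

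**The case against.** The case against making much of this is substantial.

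- **The harm is assumed.** The documents give no cohort shift, regional gap or change in mix. Eligibility is common to all cohorts, baseline viral load is in the model, and virology samples go to the sponsor or a designee (protocol 7.3.2). These limit drift but do not show that it is absent.
- **Pooling is open and deliberate.** The plan states it consistently and shows the power it buys, 80% against 59%. This stands, and pooled placebo should stay primary.
- **The plan does not rank doses.** The committee endorses the next dose on safety and available PK data (protocol 3 and 5.1.1), and SAP 4.1 looks to the totality of the data. A reader might infer that the trial would pick the dose with the largest pooled estimate, and so pick wrongly. No text says so, and the ranking probabilities only illustrate exposure to a shift.
- **Cohort data are not hidden.** Every subject's viremia is listed and plotted (SAP 8.1.2), and the sponsor may take a snapshot after each cohort (protocol 5.4.1). That is true, but neither is a specified cohort summary.
- **The own-cohort table is weak.** With 5 placebo subjects per cohort it raises more false signals than the pooled analysis and ranks a clearly better dose less reliably. This stands, and it limits what the table may be used for.

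**Conclusion.** The point holds as a vulnerability in a descriptive dose-finding analysis, not as a demonstrated error. The text establishes that the stratification factor is missing from the primary model, that a comparison quoted for power is never specified as an analysis, and that no virology summary splits placebo by cohort. The 2d/3, −d/3 and d results follow from the planned 15:5 allocation, but every log10 figure for bias depends on an assumed shift.

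Three stronger readings are tempting and should be resisted:

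- **That pooled placebo is the wrong primary comparator.** At the shifts considered it has the smaller mean squared error.
- **That false signals rise across the board.** The rate averaged over doses moves only from 0.137 to 0.145 or 0.167; the rise is confined to the shifted dose.
- **That the by-visit fallback in SAP 8.1.1 needs rewriting because its one-way ANOVA drops baseline.** It applies only if the independent-covariance fit also fails. That fit is in effect ordinary least squares and will practically never fail.

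The change is worth making because it is cheap and, if fixed before unblinding, prespecified.

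**What to change.** 1. **SAP 8.1.1.** Add geographic region as a fixed main effect, with a rule for collapsing sparse regions set before unblinding. Keep pooled placebo as the primary comparator. If region explains nothing, the SE of a dose contrast rises by about 1% with two regions and 4% with five (the visible text does not give the number). A main effect removes only a regional gap that is constant over visits. If the gap exists on Days 2–5 only, then under the assumptions of step 3 (nine post-baseline visits, serially correlated errors) 0.07–0.19 of the 0.13–0.27 bias remains, and a bias of opposite sign of 0.04–0.12 appears at later visits.
2. **SAP 8.1.2.** Add one descriptive table with placebo mean change by cohort and each regimen against its own cohort's placebo at each visit. Label it as able to show only gross disagreement, and as not for ranking doses or finding signals; the figures in step 4 are the reason.

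The cost is SAP wording, one model term and one table. No new subjects, visits or samples are needed.
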